5. STUDY DESIGN

The PiLOT-AF study is a prospective single-centre randomized observational study aiming at comparing different RF settings during AF ablation on the LA posterior wall, in terms of oesophageal heating, acute and long-term procedure success and procedural complications.

Patients, age 18-80, scheduled for their first RF ablation because of a history of symptomatic and drug-refractory paroxysmal or persistent atrial fibrillation, will be considered for inclusion in the study.

Potential subjects will initially be approached 4-6 weeks before their ablation procedure, in order to give the patients enough time to consider the information, to ask questions to the Investigator, their GP or other independent parties to decide whether they wish to participate in the study or not.

For those interested in participation, a baseline assessment will be arranged to coincide with their standard pre-admission visit, for informed consent, screening and eligibility assessment and randomization.

All AF ablation procedures will be performed in a standard fashion, under general anaesthesia and with continuous oesophageal temperature monitoring using a sinusoidal multi-sensor oesophageal temperature probe (CIRCAtemp). After LA geometry reconstruction using 3-dimensional electroanatomical mapping EnSite Velocity and a multipolar circular mapping catheter St Jude Medical Optima, a CF ablation catheter Endosense TactiCath through a deflectable sheath St Jude Medical Agilis will be used for PVI. Standardized RF settings will be used during ablation on the LA anterior wall as current practice in our centre. Different RF settings will be used on the LA posterior wall, according to randomization group. Duration of RF delivery on the LA posterior wall will be dictated by achievement of target LSI or oesophageal temperature rise $> 39^{\circ}\text{C}$ during ablation. PVI will be achieved and confirmed after 30 minutes waiting time. In case of acute PV reconnection, ablation at sites of breakthrough signals will be performed in order to achieve durable PVI. The occurrence of acute PV reconnection with sites of breakthrough signals on the LA posterior wall will be recorded for each procedure. The total procedure and RF ablation times will be also collected.

After the ablation, before discharge the symptoms status and heart rhythm will be assessed and the patient will be instructed to commence a symptoms diary. Telephone follow-ups will be then performed at 3 and 6 months to assess current symptom status. Standard care follow-up Arrhythmia Clinic visits will be also performed 3-4 months after the ablation procedure. Ad hoc visits and/or additional investigations as prolonged ECG monitoring will also take place, dictated by arrhythmia symptoms and assessment for potential adverse events related to the procedure, in accordance with standard practice.

The end of the study for each patient will be the date of the 6 months telephone follow-up.

A flowchart of the study design, indicating the time points and procedures, is shown in Appendix 1.

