1. SYNOPSIS

Study Title	Radiofrequency Power, Lesion Size Index and Oesophageal Temperature alerts during Atrial Fibrillation ablation: a pilot study	
Internal ref. no. / short title	PiLOT-AF study	
Study Design	Prospective, randomized, single centre observational clinical investigation	
Study Participants	Patients admitted for elective radiofrequency (RF) ablation for paroxysmal or persistent atrial fibrillation (AF)	
Planned Sample Size	80 patients (pilot study)	
Planned Follow-up duration	6 months	
Planned Study Period	15 months	
	Objectives	Outcome Measures
Primary	Assessment of the risk of oesophageal damage associated with radiofrequency (RF) ablation on the left atrial (LA) posterior wall when using different power settings	Luminal oesophageal temperature rises > 39°C during RF application on the LA posterior wall as recorded by an oesophageal temperature probe
Secondary	
Comparison of oesophageal complications with the different RF settings on LA posterior wall
 
Comparison of acute and short-term procedure success using different RF settings on LA posterior wall as marker of lesion transmural and durability
	
Symptoms of oesophageal injury during 6 months follow-up
 
Rate of first-pass pulmonary vein isolation (PVI), rate of acute pulmonary vein reconnection (PVR), total procedure time and RF time of the index ablation procedure
 
AF-free survival during 6 months follow-up

Tertiary	Comparison of rate of procedural complications using the different RF settings	pericardial effusion, TIA/stroke, phrenic nerve injury, pulmonary vein stenosis, open-heart surgery, death

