4. OBJECTIVES AND OUTCOME MEASURES

Objectives	Outcome Measures	Timepoint(s) of evaluation of this outcome measure (if applicable)

Primary Objective
 
To compare the risk of oesophageal damage associated with different RF settings during AF ablation on the LA posterior wall
	
Rate of oesophageal temperature alerts (defined as oesophageal temperature rise > 39°C) during RF ablation on the LA posterior wall
	
Index procedure

Secondary Objectives
 
1. To compare the acute success of the index AF ablation using different RF settings on the LA posterior wall
 
2. To compare the short-term success of the index AF ablation using different RF settings on the LA posterior wall
 
3. To compare the rate of oesophageal injury related to different RF settings on the LA posterior wall during the index AF ablation
	
1. Rate of first-pass PVI, rate of acute PVR related to breakthrough signals on the LA posterior wall, total procedure time and RF ablation time
 
2. Freedom from atrial fibrillation
 
3. Rate of oesophageal symptoms (difficult or painful swallowing, heartburn, acid reflux, sore throat, hoarseness, cough, nausea, vomiting, non-cardiac chest pain)
	
1. Index procedure
 
2. During the follow-up period (6 months)
 
3. During the follow-up period (6 months)

Tertiary objectives
 
To evaluate the rate of complications associated with the different RF settings
	
Pericardial effusion, TIA/stroke, phrenic nerve injury, pulmonary vein stenosis, open-heart surgery, death
	
Index procedure

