8.2.2. Screening and Eligibility Assessment

It will include:

- a. demographics;
- b. exclusion of pregnancy or breast feeding in case of child-bearing age female;
- c. detailed collection of any relevant medical history, but especially concerning AF, heart (including left atrial size and left ventricular function on most recent echocardiogram if any) or oesophageal diseases;
- d. list of current medications and antiarrhythmic drugs previously taken;
- e. current heart rhythm on 12-lead ECG.

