8.2.3. Randomisation

A block randomization, with blocks of size four, type 1234, will be used to assign each patient to one of the following four treatment arms:

- ✓ Group 1: 20 W RF power and target LSI = 4 on LA posterior wall;
- ✓ Group 2: 40 W RF power and target LSI = 4 on LA posterior wall;
- ✓ Group 3: 20 W RF power and target LSI = 5 on LA posterior wall;
- ✓ Group 4: 40 W RF power and target LSI = 5 on LA posterior wall.

Briefly, the study population will be divided into 4 blocks of 20 patients. Within each block, every patient will be randomly assigned to 1 of the 4 treatment arms by using sealed envelopes. At the end of each block of 20 patients, there will be 5 patients enrolled in each of the 4 treatment arms. At the baseline visit, following consent, the study nurse or doctor will telephone the Research Office and ask the administrator to open a sealed envelope from the current block of 20 and reveal the allocated treatment arm. The treatment will be unblinded to the investigator and blinded to the patient.

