11.2. Description of Statistical Methods

Comparison of primary, secondary and tertiary outcome measures among different treatment groups will be performed at each time point using appropriate statistical testing. In particular, ANOVA tests will be used to compare numerical variables and chi-square tests will be used to compare categorical values.

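### Freedom from AF is compared without using AF type (paroxysmal or persistent); one pre-specified stratum would give a small gain in precision at no cost

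*Combined protocol and SAP*

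**What the plan says.** Section 5 admits patients with "symptomatic and drug-refractory paroxysmal or persistent atrial fibrillation". The expected share of each type is not given.

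Section 8.2.3 allocates by blocks only: "A block randomization, with blocks of size four, type 1234, will be used to assign each patient". No stratification factor is named. After each 20 patients "there will be 5 patients enrolled in each of the 4 treatment arms", so four such sets give 20 per arm. (The section gives the block size as four and also as 20. That needs reconciling but does not affect this point.)

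Section 8.2.2 provides for "detailed collection of any relevant medical history, but especially concerning AF, heart". AF type is not listed as a variable in its own right.

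Section 4 makes "Freedom from atrial fibrillation" the only measure for the second secondary objective, short-term success. The synopsis calls it "AF-free survival during 6 months follow-up".

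Section 11.2 covers every outcome in general terms: "Comparison of primary, secondary and tertiary outcome measures among different treatment groups will be performed at each time point using appropriate statistical testing". It then names ANOVA for numerical variables and says "chi-square tests will be used to compare categorical values". Neither 11.2 nor 11.3 mentions a covariate, a stratified test, a model or a breakdown by AF type.

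**The concern.** Neither the design nor the analysis makes use of AF type. If patients with persistent AF recur more often, two things follow. Outcome variation that AF type could explain stays in the error term, so the comparison is less precise than it could be. And if one arm happens to draw more persistent patients, its raw AF-free proportion is pulled down for a reason unrelated to the RF settings.

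Section 3.4 reads 6-month freedom from AF as the clinical sign that lesions last, and wants the pilot to help choose a power and LSI and to size a main study. A shifted estimate could feed into both. If nothing is pre-specified, the choice to adjust may also be made after the imbalance and the results have been seen.

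**Working it through.** **Inputs from the documents.** Four arms, 80 patients, 20 per arm (8.2.3, 11.1). The total can be reproduced: 12 patients with an alert per arm ÷ 0.60 = 20, and 4 × 20 = 80. The 60% is implied; Section 11.1 states 55-75%.

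**Assumptions, not in the documents.** Persistent share 30-50%. AF freedom lower in persistent AF by 15 to 35 points, except where another gap is given. Two-sided 5% level.

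**1. How often does AF type differ between arms?** With X₁ and X₂ each Binomial(20, 0.5), a 20-point difference is 4 patients.
- A given pair of arms: P(|X₁ − X₂| ≥ 4) = 27%. For 30 points (6 patients) it is 8%. With 30% persistent, the 20-point figure is 23%.
- Highest against lowest of all four arms: 68% for 20 points or more and 30% for 30 points or more. These describe the most extreme pair, not a typical comparison.
- Two groups of 40 (for example both 20 W arms against both 40 W arms): 9% for 20 points or more.

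**2. How far does an imbalance move the estimate?** Shift = imbalance × gap by type.
- 0.20 × 15 = 3 points.
- 0.20 × 35 = 7 points.

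**3. How does that compare with sampling error?** At 70% AF freedom (assumed), the 95% half-width is 1.96 × √(2 × 0.7 × 0.3 / n).
- n = 20 per arm: 28 points.
- n = 40 per group: 20 points.

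**4. How much variance does AF type explain?** Share = p(1 − p) × gap² / [m(1 − m)], with p the persistent share and m the overall AF-free proportion. With p = 0.5, 80% v 60% AF freedom and m = 0.7: 0.25 × 0.04 / 0.21 = 4.8%. The half-width would fall from 28.4 to 28.4 × √(1 − 0.048) = 27.7 points. Over gaps of 10 to 30 points the share is about 1-10%.

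**5. Is the unadjusted test valid?** Four arms of 20 were simulated with no true effect and AF freedom of 80% in paroxysmal and 70%, 60% or 50% in persistent AF (40,000 runs per scenario). Rejection rates:

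| Randomisations considered | Unadjusted chi-square | Stratified by AF type |
|---|---|---|
| All | 4.9-5.1% | 4.6-4.7% |
| Four-arm range ≥ 25 points (40-49% of randomisations) | 5.0-6.2% | 4.5-4.8% |
| Four-arm range ≥ 40 points (4-8% of randomisations) | 4.8-8.7% | 3.9-5.4% |

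**6. How much power does stratifying add?** Two groups of 40, half persistent, unstratified test against Mantel-Haenszel (100,000 runs each). Rates are AF freedom in the better/worse group.

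| Gap by type | Paroxysmal | Persistent | Unstratified | Stratified |
|---|---|---|---|---|
| 15 | 80/60% | 65/45% | 46% | 46% |
| 25 | 85/65% | 60/40% | 46% | 48% |
| 25 and 30 | 85/65% | 60/35% | 55% | 58% |
| 35 | 85/65% | 50/30% | 46% | 49% |
| 35 | 90/70% | 55/35% | 46% | 51% |

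The gain is about 0 to 3 points in four settings and about 5 in the last. At 20 v 20, the 15-point setting shows no gain (about 26% v 25%), and the 85/65%, 60/35% setting gains about 1.5 points.

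**The case against.** The strongest objection is that randomisation already deals with chance imbalance. The chi-square test allows for it, and its error rate stays at about 5% over all randomisations. That stands. A reader might infer from the unstratified design that imbalance in AF type makes the test invalid, or that it will readily pass for an effect of the RF settings. Step 5 does not bear this out: the false-positive rate rises noticeably only after a rare, large imbalance, and even then to at most 8.7% under the strongest assumed gap.

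It can also be said that the gain is negligible beside a 28-point half-width, that freedom from AF is one secondary outcome in a pilot, and that nothing in the documents says AF type predicts recurrence. All of this stands, and it limits the importance of the point. A gain of about 8 points of power (46% to 54%) can be produced, but it needs a gap by type of about 45 points, outside the range used here.

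Finally, 11.2 promises appropriate testing without tying chi-square to this outcome by name, and the synopsis label suggests a time-to-event measure. A reader might therefore ask for a stratified log-rank test or a Cox model. That is a separate change, which the binary-outcome calculations above do not support. Event times would come from a diary, two telephone calls, one clinic visit and symptom-driven monitoring (8.4 to 8.6).

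What the objection does not remove is that the stratified test holds its error rate, needs one baseline item, and settles the adjustment before the data are seen.

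**Conclusion.** The point holds as a minor improvement in precision and interpretability. The planned comparison is valid, but it ignores a baseline factor that is cheap to use. If half the patients have persistent AF and AF freedom differs by 15 to 35 points between types, a 20-point imbalance between a given pair of arms (about 27% chance of at least that much) moves their difference by 3 to 7 points, roughly a tenth to a quarter of the 28-point half-width (3/28 = 0.11; 7/28 = 0.25). The power gain is nil at the low end of that range and 3 to 5 points at the high end for 40 v 40, a contrast that 11.2 does not itself name. If AF type is not prognostic, there is nothing to gain and very little to lose. Imprecision from small arms remains the main limit on this outcome.

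**What to change.** - **Section 8.2.2:** list AF type (paroxysmal or persistent) as a named baseline variable, and show it by arm in the baseline table.
- **Section 11.2:** state that freedom from AF at 6 months will be compared with a Cochran-Mantel-Haenszel test stratified by AF type, or a model with AF type as the single covariate. Report adjusted differences between arms with 95% confidence intervals, which suit a pilot better than p-values alone.

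The cost is one case report form item, probably already captured in the AF history, and one line of analysis text. Sample size, visits, randomisation and treatment are unchanged.

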6. STUDY RISKS AND BENEFITS

6.1. Study risks

The patients taking part will be undergoing a standard AF ablation on the basis of clinical reasons (symptoms and no response to medical therapy). When compared with the ablation protocol currently used in our centre, the study ablation protocol differs only for the use of predefined RF powers and target LSI values during PV encirclement on LA posterior wall. All proposed values of RF power and LSI have been already tested and approved in preclinical and clinical studies. Therefore no additional risks are expected from the study procedure.

Standard risks associated with an AF ablation procedure in our centre:

- bruising in the groin, mild chest discomfort, a sore throat and palpitations, which are usually self-limiting, occur in 1 in 10-20 people
- femoral vascular injury requiring a minor surgical repair occurs in 1 in 200 people;
- cardiac perforation requiring a drain at the time of the operation occurs in 1 in 50-100 people;
- pulmonary vein stenosis requiring treatment is 1 in 500;
- TIA or stroke is approximately 1 in 200 people;
- needing urgent open-heart surgery is 1 in 500 people;
- fatal complication is estimated to be 1 in 1000 people;
- cancer secondary to fluoroscopy exposure during the AF ablation is negligible considering the average low radiation dose and the short fluoroscopy time used.

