3.4 Research questions

On these premises, our research questions are:

- is it better to use higher RF powers for shorter times, than lower RF powers for longer times, to reduce the risk of oesophagus overheating and oesophageal temperature alerts?
- is the suggested LSI value of 5 on the LA posterior wall feasible or thwarted by frequent occurrence of temperature alerts leading to premature termination of RF delivery, regardless of maximum power?
- what is the impact of the different RF energy settings on PVI, acute pulmonary vein reconnection (PVR) and short-term clinical success of the AF procedure?
- which LSI value and RF power should be used during RF ablation on the LA posterior wall in order to achieve the best compromise between safety from oesophageal damage and lesion transmuralty and durability?

To these aims, the PiLOT-AF study aims to test different combinations of RF power and LSI during PV encirclement on LA posterior wall.

The rate of oesophageal alerts will be collected and compared for each procedure modality. The rate of first pass PVI and acute PVR (related to breakthrough signals on LA posterior wall), the procedure duration and RF ablation time will be also collected as clinical indicators of lesion transmuralty and acute procedure success. The freedom from AF at 6 months follow-up will be used as clinical indicators of lesion durability and short-term procedure success. The occurrence of any oesophageal symptoms at follow-up will be recorded as surrogate clinical indicators of oesophageal damage. All other procedural complications will be also recorded as safety outcomes.

No data are currently available on this topic. Therefore, this study has been designed as pilot study for power analysis and sample size calculation of a further main study.

This pilot study will hopefully give us some insights about the best combination of RF power, application time and target LSI to use during AF ablation on the LA posterior wall in order to achieve durable PVI with minimal risks of oesophageal damage.

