8.4. Pre-discharge review

As part of standard care, each patient will be reviewed the day after the ablation procedure, before discharge. The current symptoms status and occurrence of any procedural complications will be investigated and an ECG will be performed to check the heart rhythm. As part of the research study, the patient will be advised to commence a symptom diary where to record occurrence of palpitations and/or any other cardiovascular symptoms as well as oesophageal symptoms (difficult or painful swallowing, heartburn, acid reflux, sore throat, hoarseness, cough, nausea, vomiting, non-cardiac chest pain).

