8.8. Definition of End of Study

The end of study will be the date of the last 6-month telephone follow-up.

9. INTERVENTION: AF ablation

As current practice in our centre, all AF ablations will be performed under general anaesthesia and on uninterrupted therapeutic anticoagulation with warfarin (target INR 2-3 in the last 3 weeks at least) or one of the new non-Vitamin K anticoagulant drugs. A heparin infusion will also be administered during the procedure, with target Activated Clotting Time (ACT) values of 300-350 sec. Fluoroscopy and tri-dimensional electroanatomical mapping will be used by the operator, as usual, as anatomical guide during the procedure.

The procedure critical steps can be detailed as follow:

- *General anaesthesia and TOE.* After general anaesthesia and oro-tracheal intubation, a trans-oesophageal echocardiogram (TOE) will be performed to rule out the presence of thrombus in the LA appendage.

- *Vascular access, coronary sinus catheter placement and LA access.* Venous femoral access will be achieved and a deflectable decapolar diagnostic catheter placed to the coronary sinus. One or two atrial trans-septal punctures will be performed under TOE-guidance. The choice of the trans-septal kit (needle and sheath) and of the number of performed trans-septal punctures will be left to the operator.

- *Luminal oesophageal temperature monitoring.* After the trans-septal puncture(s), the TOE probe will be taken out. A two-plane sinusoidal oesophageal temperature probe, CIRCA's S-Cath (CIRCA, Englewood, CO) will be placed orally to the oesophagus and advanced to the level of the LA. It will be connected to a dedicated CIRCA Temperature Monitor (CIRCA, Englewood, CO), displaying graphically and numerically temperature data from all 12 sensors, updated 20 times per second. Any luminal oesophageal temperature rise $\geq 39^{\circ}\text{C}$ will result in a temperature alert and cessation of RF delivery at that site.

- *LA geometry.* The LA geometry will be reconstructed using the EnSite Velocity mapping system (SJ Medical, St Paul, MN, USA) and an Optima mapping catheter (SJ Medical, St Paul, MN, USA).

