11. STATISTICS AND ANALYSIS

11.1. The Number of Participants

The PiLOT-AF study aims to give some insights about the relation among RF power, LSI and incidence of oesophageal temperature alerts during AF ablation on the LA posterior wall. In view of the absence of data on this topic, it has been designed as pilot study for power analysis and sample size calculation of a further main study.

As suggested before for pilot studies (38), we aim to a final sample size of 12 patients with primary outcome data per each treatment group. We know from previous studies that oesophageal temperature alerts occur in 55-75% of AF ablations. Therefore, if taking into account also participants who do not experience oesophageal temperature alerts during AF ablation, we plan to recruit a total of 80 patients in order to achieve primary outcome data in 12 patients per group.

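### Secondary outcome 3 has no timing rule, so brief throat and chest symptoms that the protocol expects after any ablation count as oesophageal injury

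*Combined protocol and SAP*

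**What the plan says.** Section 6.1, listing the standard risks of AF ablation at the centre, states that "bruising in the groin, mild chest discomfort, a sore throat and palpitations, which are usually self-limiting, occur in 1 in 10-20 people". These are risks of the procedure as such, not of any one RF setting.

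Section 4 sets secondary objective 3, the comparison of oesophageal injury between RF settings, and measures it by "Rate of oesophageal symptoms (difficult or painful swallowing, heartburn, acid reflux, sore throat, hoarseness, cough, nausea, vomiting, non-cardiac chest pain" over the 6-month follow-up. Section 3.4 says that any such symptom will be read as a surrogate for oesophageal damage.

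At the review on the day after ablation, "the patient will be advised to commence a symptom diary" (Section 8.4). Its entries are collected at the 3- and 6-month telephone calls (Section 8.6), and Appendix B also shows collection at the clinic visit.

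Section 9 applies to every arm: "After general anaesthesia and oro-tracheal intubation, a trans-oesophageal echocardiogram (TOE) will be performed". An oral temperature probe is then passed into the oesophagus.

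The protocol gives no rule on when a symptom must begin, how long it must last, how severe it must be or what caused it. Screening (Section 8.2.2) asks about oesophageal disease but plans no record of baseline symptoms.

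**The concern.** Sore throat appears in Section 6.1 as an expected, usually short-lived effect of the procedure and in Section 4 as evidence of oesophageal injury. Mild chest discomfort and non-cardiac chest pain overlap in the same way, though the terms are not identical. Recording begins when such effects are most likely to be present, and nothing separates them from thermal injury.

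A baseline symptom record would not solve this, because these symptoms are new after the procedure. No endoscopy is scheduled, so symptoms are the only planned follow-up measure of oesophageal injury. If part of the count is procedural background shared by all arms, the reported rate is too high as an injury rate, and relative comparisons between RF settings are pulled towards no effect.

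**Working it through.** **The plan's own figure.** The only sample-size figure is for temperature alerts: "we plan to recruit a total of 80 patients in order to achieve primary outcome data in 12 patients per group", given that "oesophageal temperature alerts occur in 55-75% of AF ablations". With N = 4 × (12 / alert rate, rounded up), a 60% rate gives 4 × 20 = 80, so the figure is reproduced inside the stated range. The ends give 4 × 22 = 88 (55%) and 4 × 16 = 64 (75%). Symptoms play no part in this calculation, and the plan gives no rate, effect size or significance level for outcome 3.

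**Background rate b, from Section 6.1.** One rate, 1 in 10-20 (5-10%), is given for four effects listed together. Two of them, sore throat and chest discomfort, bear on the oesophageal list.
- If the rate covers the four combined, b is at most 5-10%.
- If it applies to each effect, and the two are independent (assumption), b = 1 − 0.95² = 9.75% to 1 − 0.90² = 19%.

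**Expected background cases.** At 5-10%: 20 × b = 1-2 per arm and 80 × b = 4-8 in all. The chance of at least one in an arm of 20 is 1 − 0.95²⁰ = 64% to 1 − 0.90²⁰ = 88%. On the per-effect reading the total is about 8-15 of 80.

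**Effect on a contrast.** The documents give no injury-symptom rate. As an illustration, assume p = 5% in one arm and 20% in another, with b equal in both and independent of injury. The observed rate is P = 1 − (1 − p)(1 − b). For example, at b = 5%: 1 − 0.95 × 0.95 = 9.75% and 1 − 0.80 × 0.95 = 24%. The odds ratio is then (0.24/0.76) / (0.0975/0.9025) = 2.92.

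| b | Low arm | High arm | Risk difference (points) | Risk ratio | Odds ratio | Power, 20 v 20 |
|---|---|---|---|---|---|---|
| 0 | 5% | 20% | 15 | 4.0 | 4.75 | 30% |
| 5% | 9.75% | 24% | 14.25 | 2.46 | 2.92 | 22% |
| 10% | 14.5% | 28% | 13.5 | 1.93 | 2.29 | 18% |
| 19% | 23.05% | 35.2% | 12.15 | 1.53 | 1.81 | 13% |

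Power is the normal approximation for two proportions at two-sided 0.05, a level assumed here.

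The risk difference is (p₂ − p₁)(1 − b), so it shrinks by exactly b: 5-10%, or up to 19% on the per-effect reading.

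The share of low-arm positives with background symptoms only is b(1 − p)/P. This is 0.05 × 0.95 / 0.0975 = 49% at b = 5%, and 0.10 × 0.95 / 0.145 = 66% at b = 10%.

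**The case against.** - **No section names day 1 as the start of counting.** Section 3.4 speaks of symptoms at follow-up, the calls ask about symptoms at that time, and the pre-discharge review is a separate contact for early problems. This stands in part: the day-1 start is inferred. But Section 8.6 also collects what the diary recorded, the diary begins the day after ablation, and Section 4's window is the whole follow-up. Including early symptoms is the natural reading.
- **A shared background cannot create a difference between arms.** Patients are randomised and blinded (Section 8.2.3). This stands, provided the background does not itself depend on the RF setting.
- **The absolute contrast hardly moves, and small numbers are the larger limit.** This stands. Power for the assumed contrast is only about 30% with no background at all.
- **The 1 in 10-20 rate is not a sore-throat rate.** This stands, which is why both readings are shown above.
- **The main study would not be sized on this outcome.** No section says it would be, and Section 11.1 is built on temperature alerts. This stands; the inflated rate matters as a reported pilot result.
- **Any early cut-off is arbitrary, and true thermal symptoms could begin and resolve before it.** This stands, and is the reason to keep the all-symptoms version beside the later one.

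**Conclusion.** The point holds for secondary outcome 3. As worded, it mixes expected procedural symptoms with symptoms of injury. About 1-2 such cases per arm of 20 would be expected at 5-10%. That is an upper bound if the Section 6.1 rate covers the four effects combined, and the background could be about 10-19% if it applies to each.

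Under the assumed 5% versus 20%, the odds ratio falls from 4.75 to 2.9-2.3, and roughly half to two-thirds of low-arm positives would not be injury. The risk difference loses only 0.75-1.5 points. The result is an inflated rate and diluted ratio measures, not a spurious arm effect. The primary outcome and N = 80 are untouched. The size rests on the assumed injury rates and on a background equal across arms and independent of injury.

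A reader might infer that early AF or palpitations are likewise scored as failed ablation, because Section 6.1 lists palpitations and Section 3.4 says "The freedom from AF at 6 months follow-up will be used as clinical indicators of lesion durability". The documents do not support that. No section counts palpitations as AF; they are recorded and may prompt investigation (Sections 8.5 and 8.6). No early AF rate is given, so no effect can be calculated. What is true is only that neither an early-period rule nor a definition of recurrence is stated.

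**What to change.** In Section 4, with matching wording in Section 8.4:

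- Have the diary record onset and end dates for each oesophageal symptom.
- Report secondary outcome 3 in two versions: all symptoms in the 6 months, and symptoms that begin or persist beyond a prespecified early period (for example day 7).
- Tabulate early symptoms separately by arm.
- Count any diagnosed oesophageal injury whenever it occurs.

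A rule based on dates is preferable to attribution by the investigator, who knows the allocation (Section 8.2.3).

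The cost is outcome wording and two date fields in a diary already planned; the diary form is not in the documents, so the exact change to it cannot be judged. No visit is added and no data are discarded. The downsides are fewer events in the later version and a cut-off that is a convention, so it must be fixed before the data are seen.

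For AF, at most add a sensitivity version of AF-free survival with a prespecified early period set aside, beside the all-events version. If that period ran to the 3-month contact, the remaining scheduled rhythm information would be the ECG at the 3-4 month clinic, since the 6-month contact is a telephone call. It should therefore not replace the all-events analysis.
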